24 assessed at pre-treatment, post-treatment, and then 1- and 4-months after treatment completion.

25 3. OBJECTIVES/SPECIFIC AIMS/RESEARCH QUESTIONS

26 **Purpose:** The purpose of this randomized controlled trial (RCT) is to evaluate the efficacy of five 60-minute sessions
27 of Written Exposure Therapy for Suicide (WET-S) + Treatment as Usual (TAU) compared with TAU in high-risk,
28 suicidal service members, veterans, and DEERS eligible beneficiaries with posttraumatic stress disorder (PTSD) or
29 posttraumatic stress symptoms (PTSS).

30 42. Research Aims and Hypotheses:

31 Aim 1: Determine if Written Exposure Therapy for Suicide (WET-S) reduces the presence, frequency, and severity of
32 suicidal ideation, suicide plans, suicide gestures, suicide attempts, non-suicidal self-injurious behaviors, and re-
33 hospitalization for suicidality measured by the Self-Injurious Thoughts and Behaviors Interview (SITBI; Nock et al.,
34 2007) among service members, veterans, and DEERS eligible beneficiaries admitted to an acute psychiatric
35 inpatient unit for suicidal ideation (SI) and/or attempt with posttraumatic stress disorder (PTSD) or posttraumatic
36 stress symptoms (PTSS) compared with Treatment as Usual (TAU).

37 Hypothesis 1. Compared with TAU alone, WET-S + TAU will result in significantly greater reductions in
38 suicide-related outcomes pre-treatment to 1- and 4-months follow-up.

39 Aim 2: Determine if Written Exposure Therapy for Suicide (WET-S) reduces posttraumatic stress symptoms (PTSS)
40 severity measured by the Clinician Administered PTSD Scale for DSM-5 (CAPS-5; Weathers, Blake, Schnurr,
41 Kaloupek, Marx & Keane, 2013) among service members, veterans, and DEERS eligible beneficiaries admitted
42 to an acute psychiatric inpatient unit for suicidal ideation (SI) or attempt and posttraumatic stress disorder (PTSD) or
43 PTSS compared with Treatment as Usual (TAU.)

57 Hypothesis 2. Compared with TAU alone, WET-S + TAU will result in significantly greater reductions in
58 PTSS severity from pre- to post-treatment, 1- month, and 4-month follow-up.

59
60 Aim 3: Determine if reductions in posttraumatic stress symptoms (PTSS) severity mediate the association between
61 treatment condition and suicide-related outcomes (suicidal ideation, plans, gestures, attempts, non-suicidal self-
62 injurious behaviors, and re-hospitalizations) measured by the Clinician Administered PTSD Scale for DSM-5 (CAPS-

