360 expectations in this yet unstudied population, we powered the study to detect small to medium sized effects for the group
361 by time interaction. Power was estimated using Repeated Measures and Sample Size computer software, accessible at
362 <https://rmass.org>. Assuming subject level randomization, a quadratic design matrix for the time effect, a 1-tailed alpha
363 level of .05, desired power of .80, equal sized treatment groups at baseline, an overall expected 15% attrition rate, a
364 stationary AR1 error correlation matrix starting at a modest $r = .30$, and desire to be able to detect at least a conventional
365 small to medium sized effect ($d = .35$) at the final assessment, the desired total sample size we intend to recruit is $N = 124$
366 ($n = 62/\text{group}$), a feasible recruitment goal given the targeted population.
367

368 **7.4.2 Primary (i.e., primary outcome variables) and secondary endpoints.** The primary dependent variables for suicidality
369 are the Self-Injurious Thoughts and Behaviors Interview (SITBI) interview and the Depression Symptom Index-Suicidality
370 Subscale (DSI-SS) self-report. The primary dependent variables for PTS symptoms and PTSD are the Clinician
371 Administered PTSD Scale (CAPS-5) interview and the PTSD CheckList-5 (PCL-5) self-report. Secondary endpoints
372 include associated psychopathology (severity scores on measures of depression, general anxiety, anger, and PTSD-
373 related cognitions)
374

375 **7.4.3 Data Analyses.** To examine hypothesis 1 (determine if WET-S + TAU reduces presence (past month), frequency,
376 and severity of suicidal ideation, suicide plans, suicide gestures, suicide attempts, and non-suicidal self-injurious
377 behaviors and re-hospitalizations related to suicidality relative to TAU only and hypothesis 2 (determine if WET-S + TAU

378 reduces PTS symptom severity relative to TAU only) , we will conduct intent-to-treatment (ITT) analyses including all
379 randomized participants who attend at least the first therapy session. General or Generalized Linear Mixed Effects
380 models, depending on the nature of the specific outcome, will be implemented for the primary ITT randomized
381 comparison of total CAPS-5 scores as well as SITBI variables of interest and number of subsequent inpatient
382 hospitalizations for suicidal behavior. The planned statistical design includes fixed effects for treatment (between-

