383 groups), time (within-subjects), and the group by time interaction. This latter effect captures differences in changes over
384 time between the groups; as such it is the effect of substantive interest in each of the models that will be examined.
385 Advantages of the general(ized) linear mixed effects model include the ability to include cases with missing data
386 (assumed missing at random), flexible specification of the covariance structure among the repeated measures, the ability
387 to model nonlinear trajectories of change over time, and the ability to perform between- and within-groups contrasts both
388 at and across assessments to examine significant group by time interactions. Prior to performing statistical analyses, the
389 data will be inspected to determine the advisability of scale transformation to normalize distributions (where applicable)
390 or reduce variance heterogeneity and to identify missing data, outliers, or other unusual features that may be influential.
391 To test hypothesis 3, growth curve modeling will be used to examine mediation. Specifically, treatment condition will be
392 entered as a predictor of change in both PTS symptom severity and suicide related outcomes. To achieve mediation,
393 WET-S +TAU would achieve superior reductions in suicide related outcomes and PTS symptom severity relative to TAU
394 only. Finally, we will examine the indirect effect of treatment condition on suicide related outcome change via PTSD
395 symptom change. Identification of an indirect effect would allow us to conclude that WET-S + TAU's superior effect on
396 suicide risk relative to TAU only is mediated by changes in PTS symptoms.
397

398 **7.7 Confidentiality.** All video telehealth therapy sessions and interview assessments will be conducted in private offices
399 in the CRDAMC acute inpatient psychiatry unit and then via video telehealth from a private location of the participant's
400 choosing once the participant is discharged from inpatient care. All assessment interviews and WET-S treatment
401 sessions speaking with the therapist will be recorded using an audio-recorder external to the HIPAA compliant telehealth
402 platform. Recordings will be labeled with the participant's study ID number.
403 The recordings will be uploaded to a secure password protected server immediately after the session is completed. The

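### The inputs listed in 7.4.1 do not deliver the stated .80 power for a group-by-time effect of d = .35 at N = 124, and the 1-tailed alpha is attached to no named contrast

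*Combined protocol and SAP*

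**What the plan says.** Section 7.4.1 describes its target this way: in view of tempered "expectations in this yet unstudied population, we powered the study to detect small to medium sized effects for the group" by time interaction. The calculation used repeated-measures sample-size software. The listed inputs begin "Assuming subject level randomization, a quadratic design matrix for the time effect, a 1-tailed alpha" and continue "level of .05, desired power of .80, equal sized treatment groups at baseline, an overall expected 15% attrition rate". They end with stationary AR1 errors at a correlation of .30, which the plan calls modest, and d = .35 "at the final assessment, the desired total sample size we intend to recruit is" 124, or 62 per group.

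Section 7.4.3 plans general or generalized linear mixed models with group, time and their interaction. It says of the interaction that it captures differences in change over "time between the groups; as such it is the effect of substantive interest in each of the models that will be examined". It counts the handling of incomplete cases as a strength: "Advantages of the general(ized) linear mixed effects model include the ability to include cases with missing data". It mentions contrasts at and across assessments but names none, and it gives no alpha or sidedness.

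The visit schedule is given outside 7.4.1:
- The abstract lists four assessments: pre-treatment, post-treatment, 1 month and 4 months.
- Hypothesis 1 concerns change in "suicide-related outcomes pre-treatment to 1- and 4-months follow-up", which is three time points.
- Hypothesis 2 adds post-treatment, which makes four.
- Figure 1 shows only self-report measures at post-treatment, whereas CAPS-5 and SITBI are interviews.

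**The concern.** The .80 figure is the stated basis for N = 124, so a reader should be able to recover it from the inputs beside it. A d of .35 at one visit is hard to detect with about 53 completers per arm, and at a correlation of .30 a contrast that subtracts baseline usually loses precision. Section 7.4.1 also leaves out the contrast, the number and spacing of visits, the course of the effect before the final visit, the timing of attrition and any random-effect variance.

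Two things are at stake. If the figure is too high for the contrast finally tested, a null result could be misread as evidence against a small-to-medium benefit. And with no contrast or sidedness named in 7.4.3, the decisive test stays open until the data are seen.

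**Working it through.** **Inputs from 7.4.1:** one-sided alpha .05 (z = 1.645), 62 per group, 15% attrition, AR1 r = .30, d = .35 at the final visit. With 15% loss, 124 × .85 / 2 = 52.7 per group.

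**Assumptions added because the plan is silent:** 3 or 4 equally spaced visits, d in total-SD units, no random effects, no true baseline difference but a baseline group term left free in the model. Attrition is taken in three ways: 52.7 per group at every visit (flat), loss rising evenly to 15% with partial data kept (gradual), or none.

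**Formula.** The vector of group differences has covariance 2R/n, with R = .30^|lag|. For a 1-df contrast estimated by generalized least squares, power = Φ(.35/SE − 1.645).

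**Attempt to reproduce .80 at N = 124**

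*Final-visit difference.* SE = √(2/52.7) = .1948. Then .35/.1948 = 1.797, and Φ(1.797 − 1.645) = Φ(.152) = .56. With no attrition, SE = √(2/62) = .1796, .35/.1796 = 1.949, and Φ(.304) = .62. Two-sided at 52.7 per group it is about .44.

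*Baseline-to-final change, 3 visits.* The lag-2 correlation is .30² = .09, so SE = √(2 × (1 − .09) × 2/52.7) = .2628. Then .35/.2628 = 1.332, and Φ(1.332 − 1.645) = Φ(−.313) = .38.

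*Step (full effect from the first post-baseline visit), 3 visits.* SE = .2159. Then .35/.2159 = 1.621, and Φ(1.621 − 1.645) = Φ(−.024) = .49.

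The same method gives, for 3 / 4 visits:

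| Test at d = .35 | Flat | Gradual | None |
|---|---|---|---|
| Change | .38 / .36 | .40 / .38 | .42 / .40 |
| Slope, linear course | .38 / .37 | .40 / .39 | .42 / .41 |
| Step | .49 / .51 | .53 / .56 | .55 / .57 |
| Quadratic interaction, 2 df, linear course | .20 / .20 | .22 / .21 | .23 / .23 |
| Quadratic interaction, 2 df, step course | .29 / .28 | .32 / .31 | .33 / .32 |
| Final visit | .56 / .56 | .56 / .56 | .62 / .62 |

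No entry reaches .80, so the choice between 3 and 4 visits does not explain the gap.

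**What does bring power near .80**

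- *Random intercept with variance share s*, so R = s + (1 − s) × .30^|lag|. The step contrast reaches .80 at s of about .46 to .58; change or slope needs .66 to .73. At s = .5 the total lag-1 correlation is .5 + .5 × .30 = .65.
- *Correlation indexed in months, 4 visits, full effect at post-treatment.* The step contrast has .82 to .90 if post-treatment falls 7 to 8 days after baseline, and .67 to .73 at 14 days. With three visits it is only about .47 to .54.
- *No baseline group term.* A step effect gives .74 to .89, including .802 at exactly 62 per group with 3 visits and no attrition; with the listed 15% loss that 3-visit case gives .74 to .77. A slope model with a step course and 4 visits gives .78 (gradual) or .82 (none).
- *Time-averaged group effect:* .83 to .93. This is not an interaction.
- *A lag-1 correlation of .70 instead of .30:* step .76 to .82.

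**Sidedness.** A quadratic time matrix gives the group-by-time effect two components, linear and quadratic, hence 2 df. A joint 2-df test has no direction. Hypotheses 1 and 2 are directional, so a 1-tailed test is possible, but only for one named contrast.

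**Effect detectable at 80% with 124 and 15% loss, one-sided:** (1.645 + .842) × SE gives about .49 to .54 for the step and .63 to .68 for slope or change. For the final visit it is 2.487 × .1948 = .48. Two-sided, the final visit gives (1.960 + .842) × .1948 = .55.

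**The case against.** The best reply is that zero random-effect variance is the reviewer's assumption. Section 7.4.3 plans mixed models, and 7.4.1 applies AR1 to the errors, which leaves room for a subject effect. Some further inputs must also have been entered, because repeated-measures power cannot be computed without a visit count and an effect course. This stands. It is why the low figures are illustrations, and a reader who infers that the trial has 36% to 57% power goes further than the documents allow. It does not rescue the stated figure: no variance share is given, and a total lag-1 correlation near .65 sits badly with a correlation described as modest at .30.

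A reader might also infer that the software run was wrong, or that the routes above are the only ones to .80. Neither is supported. The settings and output are not in the documents, and the list is not exhaustive. The plan's wording that the correlation starts at .30 could even mean the low end of a range, though a lag-1 value is the more natural reading.

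Two further replies are partly right. The number of visits is missing from 7.4.1 but can be found elsewhere, and neither count restores .80. Section 7.4.1 does not state an omnibus 2-df test, and placing d at the final assessment suggests a directional 1-df reading; but that comparison gives .56 to .62, and the contrast is still not named.

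Finally, the plan expects a much larger effect. That is so, but it chose d = .35 as the conservative basis for N = 124, and this point concerns only that claim.

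**Conclusion.** The point holds as a power figure that its own listed inputs do not support. Under equally spaced visits, no random effects and d in total-SD units, matched one-sided interaction contrasts with a free baseline difference give about .36 to .57 against the stated .80, and the final-visit comparison gives .56 to .62. Confidence is high that .80 does not follow from what 7.4.1 lists. It is not high for any particular true power, which depends on inputs that are not written down. Separately, the 1-tailed alpha has no defined test until a 1-df contrast is named, and 7.4.3 supplies neither contrast nor sidedness. This should be fixed; it does not call N = 124 itself into question.

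**What to change.** Keep N = 124.

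1. Name one directional group-by-time contrast, with its degrees of freedom and sidedness, and use it in both 7.4.1 and 7.4.3.
2. In 7.4.1, state the number and spacing of visits by instrument, the assumed effect course, attrition by visit and any random-effect variance. Figure 1 shows self-report only at post-treatment, so reconcile it with Hypothesis 2, which counts post-treatment for CAPS-5.
3. Rerun the power once. If .80 is reproduced for the named contrast, report the inputs and keep the figure. If not, replace the .80 claim with the power and detectable effect that 124 delivers. For reference only, since it is not the group-by-time effect, a final-visit difference with 15% loss reaches 80% power at d of about .48 one-sided or .55 two-sided.

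The cost is some text and one rerun of the software, with no added participants or visits. The downside is that the stated power may become less favourable.

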90 Suvak, Wisco, Marx, & Resick, 2013; Bryan et al., 2016); however, it is challenging to provide most of these
91 treatments to high-risk service members on an acute inpatient unit because they require more time and resources
92 than are typically afforded during inpatients stays. This means that those with PTSD who are at highest suicide risk
93 are not receiving treatment for PTSD until they are discharged from the hospital and there is no available evidence to
94 suggest that treatment as usual in inpatient psychiatric settings reduces the likelihood of suicide after discharge.

95
96 WET is a 5-session treatment that is included in the 2017 VA/DoD Clinical Practice Guidelines for managing PTSD
97 (2017). WET is associated with large within- and between-group effect sizes that are comparable with other
98 evidence-based PTSD treatments (Sloan, Marx, et al., 2018). Sloan and colleagues (2012) examined the efficacy of
99 WET relative to wait list (WL) comparison condition delivered to men and women who had a diagnosis of PTSD
100 related to a motor vehicle accident. Intent to treat findings indicated a very large between group differences (Cohen's
101 d = 2.49 and 2.19 at post-treatment and 3-month follow-up, respectively), with 91% of participants no longer meeting
102 diagnostic criteria for PTSD 6 months following treatment (Sloan et al., 2012). Moreover, WET was associated with
103 low attrition (n = 2; 9%) and high treatment satisfaction ratings. Next, WET was compared with Cognitive Processing
104 Therapy for PTSD, a first- line PTSD treatment that is much more time intensive than WET, in a non-inferiority trial.
105 Participants in both treatments displayed a significant reduction in PTSD symptom severity (large within group effect
106 sizes). However, a significant treatment condition difference in dropout was also observed, with 39% dropout in CPT
107 compared with 6% in WET (Sloan et al. (2018)). Thus, WET may overcome many implementation challenges in an
108 inpatient acute care treatment setting (e.g., minimal therapist-patient contact, nominal time needed to train therapists,
109 treatment brevity, and low attrition). Preliminary data suggest that WET also reduces suicidal ideation. Specifically,
110 secondary analysis of data from the WET vs. CPT study sample demonstrated that among those who received WET
111 and who endorsed SI at baseline (n = 18 of 63; 28.57%), a significant effect of linear time was observed (B = 0.338,

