267 sessions will be provided to ensure the rationale of WET-S as a treatment for PTSD is understood by the participant
268 and to allow for a full course of WET-S sessions. WET-S will be delivered in a condensed or "massed" treatment
269 format, consisting of at least one WET-S session each day until the treatment is complete. For some participants,
270 two WET-S sessions per day may be considered to complete the protocol prior to discharge if possible. However, if
271 participants are discharged from inpatient care prior to completing the WET-S protocol, WET-S will continue using a
272 secure HIPAA-compliant video telehealth platform.
273

274
275 WET-S treatment also includes the development and monitoring of a Crisis Response Plan (CRP) for suicide risk.
276 Participants assigned to WET-S will complete the CRP prior to beginning their writing in session 1. Patient use of the
277 CRP since the previous session will be briefly reviewed at the start of each WET-S session to manage safety and
278 problem solve fluctuations in risk during treatment.
279

280 Treatment As Usual (TAU). The TAU condition consists of daily contact and patient centered care by the acute
281 psychiatric inpatient unit provider team (e.g., psychiatrists, therapists, case managers, behavioral health techs). TAU
282 includes initial psychiatric stabilization, nurse case management, medication management, psychoeducation groups,
283 and discharge planning. Patients engage with the provider team daily and have structured times for psychoeducation
284 groups, case management, medication management, hygiene, and meals.
285

286 **7.2 Drugs, Dietary Supplements, Biologics, or Devices.** N/A

320 All UTHSCSA STRONG STAR network connectivity is segmented with Access Control Lists and is not accessible to
321 any other UTHSCSA network segments. STRONG STAR data server is physically located at the Advanced Data
322 Center (ADC) has 24x7 onsite security, card key, biometric access controls and video surveillance. University of
323 Texas Health Science Center at San Antonio (UTHSCSA) ADC facility also maintains Gen 2 firewall devices to
324 protect and prohibit any unauthorized access to UTHSCSA data. All UTHSCSA network devices are monitored by
325 state-of-the-art monitoring applications that include configuration audit, management, and availability 24x7.
326

327 The UTHSCSA STRONG STAR data server is currently a VMware Instance running Windows Server 2016

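### The primary ITT set admits only randomized participants who attend a first therapy session, an event the available text defines for WET-S only, so randomization does not protect the comparison

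*Combined protocol and SAP*

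**What the plan says.** Section 7.4.3 (Data Analyses) covers hypotheses 1 and 2 with one sentence on the analysis set: "we will conduct intent-to-treatment (ITT) analyses including all" "randomized participants who attend at least the first therapy session". The same section uses this set for the primary mixed-model comparison of CAPS-5 totals, SITBI variables and re-hospitalizations. The term that decides each model is the group-by-time interaction: "as such it is the effect of substantive interest in each of the models that will be examined".

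Section 7.1.8 (Treatment Procedures) sets out numbered sessions for WET-S and describes the content of the first. It adds that "Participants assigned to WET-S will complete the CRP prior to beginning their writing in session 1".

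TAU is described differently: "The TAU condition consists of daily contact and patient centered care by the acute" "psychiatric inpatient unit provider team (e.g., psychiatrists, therapists, case managers, behavioral health techs"). Its listed elements are stabilization, case management, medication management, psychoeducation groups and discharge planning. None is named as a first therapy session.

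The available text defines no analysis set of all randomized participants and no sensitivity analysis for this exclusion.

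**The concern.** An ITT comparison is protected because nothing that happens after randomization decides who is counted. Here attendance decides, and the groups being compared are no longer the randomized groups.

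The rule is also unclear for one arm. Read literally, a TAU participant has no stated way to qualify. Read in the only way the text supports, all TAU participants stay and WET-S non-starters leave. Under that second reading the exclusion is one-sided. If people who never start WET-S would have done worse than those who start, their removal flatters WET-S; if they would have done better, it works against WET-S.

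The affected analyses are the primary ones, in a trial whose outcomes include suicide attempts and re-hospitalization. The loss cannot be repaired at the end if non-starters were never assessed.

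**Working it through.** The defect lies in a definition, so the plan has no figure of its own to reproduce. The calculation shows how large the bias could be under the one-sided reading.

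**Inputs from the documents.** 124 randomized, 62 per group (7.1, 7.4.1). One-tailed alpha .05, target effect d = 0.35 at the final assessment, 15% attrition, AR1 correlation starting at 0.30 (7.4.1). Four assessments (Abstract), of which the post-treatment one is shown as self-report only in Figure 1, leaving three for the interviews.

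**Assumptions (not in the documents).** q is the share of the WET-S arm that never attends session 1. delta is how many SD less non-starters would improve to the last visit than starters.

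**Shift.** The mean for the whole arm equals the starters' mean minus q × delta. Dropping non-starters therefore moves the estimate by q × delta towards WET-S.

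**Standard errors.** Analysed per arm: 62 × 0.85 = 52.7.
- Change from baseline to last visit: SE = √(4(1 − ρ)/52.7). Four occasions: ρ = 0.3³ = 0.027, SE = 0.272. Three occasions: ρ = 0.3² = 0.09, SE = 0.263.
- Single visit: SE = √(2/52.7) = 0.195.

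**One-tailed error when there is no true effect.** 1 − Φ(1.645 − q × delta / SE).

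| q (of 62) | delta | Shift (SD) | Share of 0.35 | Error, change | Error, single visit |
|---|---|---|---|---|---|
| 0, or delta = 0 | – | 0 | 0 | .050 | .050 |
| 5% (3) | 0.3 | 0.015 | 4% | .056 | .058 |
| 6% (4) | 0.5 | 0.030 | 9% | .062–.063 | .068 |
| 10% (6) | 0.5 | 0.050 | 14% | .072–.073 | .083 |
| 15% (9) | 0.8 | 0.120 | 34% | .114–.117 | .152 |
| 10% (6) | −0.5 | −0.050 | −14% | .033–.034 | .029 |

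The only WET losses in the documents are in section 5: 9% in the wait-list trial and 39% under CPT "compared with 6% in WET" in the non-inferiority trial. These are attrition and dropout figures, not rates of missing session 1. The 10% row is therefore towards the high end, and the 15% with 0.8 SD row is an extreme case.

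**Does relabelling suffice?** A simulation took 62 per arm, no true effect among all randomized, 15% random loss, and maximum-likelihood estimation of baseline-to-last change, with q = 10% and delta = 0.5. It used 60,000 trials (Monte Carlo error 0.001). Bias in SD for ρ = 0.027 / 0.09:
- non-starters excluded: 0.051 / 0.049
- kept with baseline only: 0.051 / 0.049
- half followed: 0.025 / 0.023
- all followed: 0.001 / −0.001

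A non-starter with only a baseline value adds almost nothing to the group-by-time contrast. The bias goes only if non-starters are followed.

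**The case against.** The strongest reply has five parts.

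- **A TAU counterpart may have been intended.** The TAU team includes therapists and TAU includes psychoeducation groups, so both arms might be filtered. The available text also lacks protocol lines 287 to 319 and the upper part of Figure 1, where a definition could sit. This stands as a caution: under such a rule the bias would depend on the difference between arms, and the table would not apply. The set would still depend on behaviour after randomization and would still not be ITT. That section 7.7 mentions recording only WET-S sessions is weak evidence either way.
- **Non-start may be rare.** Sessions are at least daily and begin on the ward. At q = 2% to 3% and delta = 0.5 the error for change is only .054 to .056. This stands.
- **The error rates are not for the planned test.** They use a baseline-to-last contrast with about 36% to 38% power at d = 0.35. The plan's stated 80% power implies SE = 0.35/(1.645 + 0.842) = 0.141, which would raise the 10%, 0.5 SD case to about .10. The figures are illustrative, and this point does not make the concern smaller.
- **Mixed models handle missing data.** The missing-at-random assumption cannot help people left out of the model, and baseline-only inclusion hardly helps.
- **Follow-up is partly covered.** Section 10.0 asks people who discontinue treatment to return, and has staff encourage follow-up when someone stops attending. That could be read to reach non-starters, but it does not name them.

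**Conclusion.** The concern holds. The plan claims an ITT analysis and defines a set that is not one, with no stated way to apply the rule to TAU. That conclusion rests on the definition and needs no assumption about q or delta.

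The size and direction of bias are unknown. Under the one-sided reading, the positive assumed cases run from 0.015 SD (error about .056) to an extreme 0.12 SD (error about .11 to .15). Bias is zero if everyone starts or if non-starters would fare the same, and negative if they would fare better. Confidence is high that the set is mislabelled and the primary comparison unprotected; one-sided bias is conditional on the reading. The point must be fixed before the analysis, and preferably while non-starters can still be assessed.

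**What to change.** In section 7.4.3:
- Define the primary set as all randomized participants (target 124), analysed in the arm assigned, whatever sessions they attended.
- Keep the attended-session-1 set as a sensitivity analysis, named as such, and state how the condition applies to TAU.

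In section 10.0:
- State that follow-up assessments are sought from participants who never start WET-S, and from those withdrawn from study treatment who have not withdrawn from the study.

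For re-hospitalization, use medical record review, already a data source in section 7.1.2, where available.

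Nothing here changes who stops treatment. The cost is wording in the protocol and SAP, plus follow-up effort for about 3 to 9 of 62 people under the assumed range. The estimate may be slightly diluted because participants who received no WET-S are counted in that arm.

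### For continuous outcomes, the planned group-by-time test in 7.4.3 is valid, but in all randomized participants it is no more precise, and usually less precise, than a baseline-adjusted contrast

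*Combined protocol and SAP*

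**What the plan says.** Section 7.4.3 uses general or generalized linear mixed models, depending on the outcome. "The planned statistical design includes fixed effects for treatment (between" groups), "time (within-subjects), and the group by time interaction. This latter effect captures differences in changes over" time, and the interaction is named as the effect of interest in every model. Contrasts at and across assessments serve to examine a significant interaction. No baseline covariate and no shared baseline mean is specified. The outcomes named are the "comparison of total CAPS-5 scores as well as SITBI variables of interest and number of subsequent inpatient" hospitalizations. Missing data and covariance are described as "assumed missing at random), flexible specification of the covariance structure among the repeated measures, the ability" to model nonlinear change, and so on.

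The analysis set is limited to "randomized participants who attend at least the first therapy session". Section 7.1.8 describes usual care this way: "The TAU condition consists of daily contact and patient centered care by the acute" inpatient team. It describes no study therapy session for that arm.

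Section 7.4.1 plans for the group-by-time effect with quadratic time, one-tailed alpha .05, 15% attrition, a "stationary AR1 error correlation matrix starting at a modest" r = .30, and d = .35 "at the final assessment, the desired total sample size we intend to recruit is" 124 (62 per group).

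Sections 7.1.5 and 7.1.6 place the baseline assessment after consent, to confirm eligibility. Section 7.1 targets 140 consented and 124 randomized.

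**The concern.** Because baseline is measured to establish eligibility, the true arm difference at baseline is zero in all randomized participants. The planned model still estimates that difference and subtracts it in full from each follow-up difference. With 62 per arm and equal SDs, the chance baseline difference has a standard error of sqrt(2/62) = .18 SD. An analysis that uses the known zero, or adjusts for the baseline score, estimates the same treatment effect with less noise in most settings. What is at stake is precision and power on the continuous outcomes, at no cost in data.

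The point covers total CAPS-5. It extends to SITBI severity, PCL-5 and DSI-SS only if they are analysed as continuous. PCL-5 and DSI-SS are primary in 7.4.2, but 7.4.3 does not name them. Binary, count and hospitalization outcomes are outside it.

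**Working it through.** **Inputs from the documents.** 62 per arm, d = .35 at the final visit, one-tailed .05, 15% attrition, AR1 .30 (7.4.1); free treatment, time and interaction effects (7.4.3).

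**Assumptions.** The SD ratio k = baseline SD / follow-up SD; the baseline-to-4-month correlation rho; dropout spread evenly over visits to 15% at 4 months; categorical visits. Both 3 visits (baseline, 1 and 4 months) and 4 visits (adding post-treatment) were run, because Figure 1 lists only self-reports at post-treatment while Hypothesis 2 includes that visit for PTSS severity.

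**The plan's own figure.** The sample size of 124 was not reproduced. A change contrast at d = .35 with complete data needs n per arm = 2 × (1.645 + .842)² × 2(1 − rho) / .35², about 184 at rho = .09 and 196 at rho = .027. A single final-visit comparison needs 101. The software settings are not in the documents, and nothing below relies on this comparison.

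**Complete-data formula.** With follow-up SD 1 and n per arm:
- change contrast: variance (2/n)(1 + k² − 2·rho·k)
- adjusted contrast: variance (2/n)(1 − rho²)
- ratio = (1 + k² − 2·rho·k)/(1 − rho²) = 1 + (k − rho)²/(1 − rho²)

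The ratio is never below 1 and equals 1 only when rho = k. With k = 1 and rho = .5 it is 1/.75 = 1.33.

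**With 15% attrition.** Using only the baseline and final visits and k = 1, the ratio is 1 + .85(1 − rho)/(1 + rho). At rho = .5 this is 1 + .85 × .5/1.5 = 1.28. Generalized least squares with the intermediate visits gives 1.29. Ratios by constant correlation:

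| rho | k = 1, complete data | k = 1, 15% loss | k = .7, 15% loss | k = 1.3, 15% loss |
|---|---|---|---|---|
| .3 | 1.54 | 1.46 | 1.15 | 1.94 |
| .5 | 1.33 | 1.29 | 1.05 | 1.73 |
| .7 | 1.18 | 1.15 | 1.00 | 1.61 |

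A k below 1 is plausible for CAPS-5, because entry requires a score above 20. As an illustration, a normal score cut at 20, with assumed mean 25-40 and SD 10-14, keeps .67-.94 of its SD.

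**Reading the planning AR1.** If AR1 .30 by visit index is the whole correlation, rho is .30² = .09 with 3 visits or .30³ = .027 with 4, and the ratio is 1.71-1.81. If a random intercept carries a share s of the variance (assumption), rho = s + (1 − s) × .09 or s + (1 − s) × .027:
- s = .3: rho .32-.36, ratio 1.40-1.45
- s = .5: rho .51-.55, ratio 1.26-1.28
- s = .6: rho .61-.64, ratio 1.19-1.21

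**Quadratic time.** With 3 visits it is saturated and nothing changes. With 4 visits the ratios are mostly smaller: 1.16-1.26 at .5 and 1.08-1.14 at .7, depending on time coding.

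**Power of a 4-month contrast** (d = .35, k = 1, 15% loss). At rho .5 the standard errors are .190 (change) and .168 (adjusted). So .35/.190 − 1.645 = .20 gives power .58, and .35/.168 − 1.645 = .44 gives .67. At rho .7 the powers are .76-.77 and .81-.82.

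**Effect of the first-session filter.** Suppose it leaves a persistent baseline difference delta between arms (assumption). Adjustment then has bias delta(1 − rho), and the change contrast has none. At rho = .5, delta of .1-.2 SD gives a bias of .05-.10 SD. With SE .168, the one-tailed type I error is about .09-.15 if the bias favours WET-S. At .2 SD the mean squared error is .10² + .168² = .038, against .190² = .036 for the change contrast.

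**The case against.** The strongest reply is that nothing here is an error. Hypotheses 1 and 2 are worded as greater reductions, the trial is powered for the interaction, and the interaction is what is tested. This stands: the plan is coherent and valid, and a reader who inferred bias or an invalid test would go beyond the documents.

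A reader might also take 1.71-1.81 as the loss implied by the plan's own inputs. The documents do not support that. Section 7.4.1 gives an AR1 matrix for the errors, 7.4.3 plans mixed-effects models with an open covariance structure, and 1.71-1.81 needs no random-effect variance at all.

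The gain may also be negligible for CAPS-5, the one score that is certainly in scope, if its baseline spread is narrowed by the entry rule and the correlation is high. The power figures concern a 4-month contrast that the plan uses to set the effect size but does not name as the sole primary test. Both limits stand.

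Finally, the adjusted model does not suit the analysis set as written, since the first-session filter may act in one arm only. That stands too, and makes the recommendation conditional. It does not remove the gain in all randomized participants. There the two contrasts have the same expected value, and the adjusted one was at least as precise in every case computed.

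**Conclusion.** The concern holds as a matter of efficiency, not validity. In all randomized participants, the planned contrast is no more precise than a baseline-adjusted one for continuous outcomes, and usually less so. Under equal SDs, categorical visits and evenly spread 15% attrition, the excess 4-month variance is about 15% to 46% over correlations .7 to .3. It shrinks to between 0% and 15% if the baseline SD is .7 of the follow-up SD, and is larger if the baseline SD exceeds the follow-up SD. The documents fix neither quantity, so no single figure can be assigned to this trial.

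A reader might infer that adjustment would restore the planned power. It does not: at correlation .5 the 4-month contrast reaches about .67, still short of .80. This is a worthwhile, optional improvement that depends on analysing all randomized participants.

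**What to change.** If all randomized participants are analysed, prespecify one of two models for the continuous outcomes and name it in advance:
1. a constrained longitudinal model with a common baseline mean and treatment-by-post-baseline-visit terms; or
2. a model of the post-baseline visits with the baseline score as covariate.

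Report the 4-month treatment difference together with each visit's estimate. State which SITBI, PCL-5 and DSI-SS scores are treated as continuous, and specify binary, count and hospitalization outcomes separately.

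If the first-session filter is kept, do not impose the common baseline. State that baseline adjustment may leave residual bias, and keep the planned change contrast, at least as a sensitivity analysis.

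The cost is a short text edit, with no new data, visits or participants and no change to the hypotheses. The real decision attached to it is the analysis set.
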